3.6 Statistical Software and Level of Significance

All statistical analyses will be performed using SAS (version 9.3 or higher) on Windows operating system. Null hypotheses tested are that there are no differences in true parameter between comparison groups, unless otherwise stated. A two-sided *p*-value of 0.05 will be used as the significance level for the determination of statistical significance in all statistical tests.

4 Statistical Analyses

The efficacy endpoints are defined as follows:

All patients:

- Change in the BAD total score from baseline (defined as prior to the start of deferiprone therapy) to Visit 4, as assessed by central evaluation of videotapes
- Proportion of patients with improved or unchanged BAD scale total score between baseline and Visit 4 (responder analysis, responders defined as change in BAD total score to be ≤ 0)
- Change from baseline to Visit 4 in BAD scale score per body region (eyes, mouth, neck, trunk, and each upper and lower extremity), as assessed by central evaluation of videotapes
- PGI-I score at Visit 4
- Proportion of patients showing an improvement on PGI-I at Visit 4 (responder analysis, responders are defined as patients whose conditions have not deteriorated; patients who have “no change”, or are “minimally improved”, “much improved” or “very much improved” in the PGI-I questionnaire at the last study visit)

The time points for these efficacy endpoints are defined as follows:

- For patients who received deferiprone in the initial study, the baseline visit of that study will be treated as the baseline visit of TIRCON2012V1-EXT as well. Thus, Visit 1 of the extension study (Week 0) will be Year 1.5 (month 18), and Visit 4 (Week 78) will be Year 3 (month 36).
- For patients who received placebo in the initial study, Visit 1 of the extension study (Week 0) will be the baseline visit. Thus, Visit 4 (Week 78) will be Year 1.5 (month 18).

Patients who received placebo in initial study:

For this group only, for each measure, the changes seen between the start and completion of the initial study (TIRCON2012V1) (i.e., following 18 months on placebo) will be compared against the changes seen between the start and completion of extension study (TIRCON2012V1-EXT) (i.e., following 18 months on deferiprone), as follows:

- Comparison of change in BAD total score from baseline to completion of the initial study vs. change in BAD total score from baseline to completion of the extension study
- Comparison of the proportion of patients with improved or unchanged BAD scale total score between baseline and completion of the initial study vs. the proportion

with improved or unchanged BAD scale total score from baseline to completion of the extension study (responder analysis)

- Comparison of the change in BAD score per body region between baseline and completion of the initial study vs. change in BAD score per body region between baseline and completion of the extension study
- Comparison of PGI-I score at the completion of the initial study vs. PGI-I score at the completion of the extension study
- Comparison of the proportion of patients showing an improvement on PGI-I at completion of the initial study vs. the proportion showing an improvement at completion of the extension study (responder analysis)

The following time window will be employed to classify the efficacy data into each scheduled visit according to the time elapsed from the first medication date (date of exposure) to the assessment date:

Month 6 visit: 3 to <9 months

Month 12 visit: 9 to <15 months

Month 18 visit: 15 to <21 months

Month 24 visit: 21 to <27 months

Month 30 visit: 27 to <33 months

Month 36 visit: 33 to <39 months

The exact calculation of time elapsed from the date of exposure to the sample assessment date is: $\text{Time elapsed} = (\text{date of sample assessment}) - (\text{date of exposure}) + 1$. The resulting time elapsed will be expressed in months and will be used for data tabulation and trend analysis. If multiple measurements for an outcome are available at the same visit for a subject, the average value will be used for that outcome for this subject at that visit.

A paired t-test will be used to assess the statistical significance of the changes in the efficacy outcomes from baseline to the end of study. For the BAD total score and for PGI-I, the proportions of patients determined to be responders at the end of study will be calculated and presented along with 95% confidence intervals.

The incidence of changes in DBS settings and outcome impacting medication use as well as the frequency of PRN drug or rescue medication use will be tabulated by visit and treatment group for patients on placebo in the initial study. The incidence of changes in DBS settings and outcome impacting medication use as well as the frequency of PRN drug or rescue medication use will be compared between the initial study and the

extension study. Continuous variables will be compared by paired t-tests while proportions by McNemar's test. If statistically significant imbalances are detected, they will be adjusted accordingly for the comparison of changes in BAD and PGI-I between the initial study and the extension study by using a MMRM model approach that is consistent with the analysis of these two efficacy measures in the initial study. The MMRM model is specified below.

The MMRM model will be applied to non-imputed data from the observed cases (OC) data set. Let y_i denote the vector of n_i continuous post-baseline measurements observed for study patient i . Each response (i.e., each element of y_i) will be defined as the patient's score at that occasion minus the baseline score.

The model will assume that the distribution of y_i is multivariate normal,

$$y_i \sim N(X_i\beta, \Sigma_i),$$

where X_i is a design matrix of dimensions $n_i \times p$, β is a vector of coefficients of length p , and Σ_i is an $n_i \times n_i$ covariance matrix.

The MMRM model will include baseline value of the outcome as a covariate and treatment group as the main factor in the model. A change in DBS settings or use of medications that have the potential to affect dystonia symptoms during the study may confound the treatment effect assessment (named outcome impacting medication use hereafter) for DFP vs. placebo between the initial study and the extension study for patients who were on placebo in the initial study. Hence, both variables will also be included in the MMRM model as visit-dependent covariates.

The visit-dependent covariate for DBS settings change is defined as follows: for patients with DBS at enrollment, if there is any DBS setting change since the previous visit, it will be coded as 'DBS Setting Change' for the current visit or 'No DBS Setting Change' otherwise. For example, if a patient has a DBS setting change between the outcome assessment dates at month 6 visit and month 12 visit, it will be coded as 'DBS Setting Change' for month 12 visit in the model. For those patients without DBS at enrollment, it will be coded as 'No DBS'. A discrete variable, DBSCHG, with three categories will be included in the MMRM model.

The visit-dependent covariate for the outcome impacting medication use will be defined according to whether the patient is on a regular dosing regimen or on a PRN (as needed) dosing regimen between two visits. For patients treated on a regular dosing regimen, if there is a dose change or starting of new medication since the previous visit, it will be coded as 'Yes' for the current visit and the future follow-up visits or 'No' otherwise in the model. For patients who do not use any outcome impacting medication, it will be coded as 'No'.

For patients on a PRN (as needed) dosing regimen, the visit-dependent covariate will be defined according to the treatment impact period in the following table.

Medication	Treatment impact period
Baclofen	30 days
Trihexyphenidyl	30 days
Clonazepam	30 days
Tizanidine	30 days
Botox	60 days
Tetrabenazine	90 days

If the PRN drug is started within the treatment impact period prior to the assessment date of an outcome for a visit, it will be coded as ‘Yes’ for that visit. If the drug is started outside this time window but is not interrupted within this period, it will also be coded as ‘Yes’ for that visit. Under other conditions, it will be coded as ‘No’ in the model. A binary variable for the outcome impacting medication use, RESMED, will be included in the MMRM model.

The frequency of PRN drug or rescue medication use between two outcome assessment dates of current visit and the previous visit will also be included in the MMRM model as a quantitative visit-dependent covariate, NDRUG, for the current visit.

The MIXED procedure in SAS will be used for the MMRM model analysis. Data within each patient at different visits will be considered repeated measures. AR(1) (autoregressive of order 1) covariance structure will be used to model the correlation between repeated measures within the same patient and Kenward and Roger’s method will be used to estimate the denominator degrees of freedom. The 95% confidence interval (CI) for the difference between the two treatments will be calculated by the LSMEANS statement.

A sample SAS code for the MMRM model is presented in the box below:

```
proc mixed;
  class TREAT USUBJID VISIT DBSCHG RESMED;
  model CHG=TREAT VISIT TREAT*VISIT BASE DBSCHG RESMED
  NDRUG/solution ddfm=kr;
  repeated VISIT/ subject=USUBJID type=ar(1);
  lsmeans TREAT*VISIT / diff cl;
run;
```

where TREAT is the indicator variable for treatment group (DFP vs. Placebo), USUBJID represents the patient ID, VISIT is the discrete variable representing the scheduled study visit after the baseline visit, DBSCHG is the discrete variable with three categories for

DBS settings change (DBS Setting Change, No DBS Setting Change, No DBS), RESMED is the binary variable for outcome impacting medication use (Yes vs. No), CHG is the change in value of efficacy outcome from baseline to the scheduled visit, BASE is the baseline value of efficacy outcome, and NDRUG is the frequency of PRN drug or rescue medication use.

PGI-I is already a measurement of change from baseline and thus will be used directly as the outcome variable and baseline BAD score will be included as the baseline value in all models.

McNemar's test will be used to compare the proportion of responders in the initial study with the proportion of responders in the extension study.

For all patients who were on DFP in both studies, the longitudinal response profile for BAD score will be explored by a MMRM model with time modelled as a continuous variable.

For this model, AR(1) (autoregressive of order 1) covariance structure will be used to model the correlation between repeated measures within the same patient and Kenward and Roger's method will be used to estimate the denominator degrees of freedom.

A sample SAS code for this MMRM model is presented in the box below:

```
proc mixed;  
  class USUBJID VISIT;  
  model BAD= TIME /solution ddfm=kr;  
  repeated VISIT/ subject=USUBJID type=ar(1);  
run;
```

where USUBJID represents the patient ID, VISIT is the discrete variable representing the scheduled study visit after the baseline visit, BAD is the value of BAD score at each time point, and TIME is the time in months at each time point corresponding to each visit.

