4.7 Rescue Medication

Rescue medication is defined as a newly prescribed medication or a change in dosage of a currently prescribed medication that has the potential to have an effect on dystonia symptoms and is provided because of a worsening of the patient's condition.

The use of rescue medication should be limited to circumstances judged as absolutely necessary by the investigator. Any use of a rescue medication must be documented, including

the reason. If a patient uses rescue medication for more than 2 events, the investigator should notify the sponsor to discuss the patient’s continued participation in the study.

Rescue medications for dystonia include, but are not limited to, the list of drugs provided in [Appendix 3](#).

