3.3 Analysis Populations

The following study populations will be used for analysis: Safety, Intent-to-Treat (ITT), and Per-Protocol (PP). The safety population will be used for the analysis of safety endpoints. The ITT population will represent the primary analysis population for the evaluation of efficacy endpoints, and the PP population will be the secondary efficacy analysis population.

Safety Population

The Safety population will include all patients who took at least one dose of study drug in the extension study.

ITT Population

The ITT population will include all enrolled patients who received at least one dose of study drug and have a baseline and at least one post-baseline efficacy assessment in the extension study.

PP Population

The PP population will include all enrolled patients who complete the extension study and have an efficacy assessment at the end of the study, have no major protocol violations, and have no change in DBS and baclofen pump settings or medications that could have an impact on dystonia. Prior to database lock, protocol deviations and medications that could have an impact on dystonia will be reviewed for their seriousness, and patients with major deviations will be excluded from the PP population.

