3.5 Missing Data Handling and Derivation Rules

For safety data analysis, no imputation will be performed on the missing data and analysis will be based on observed cases.

For efficacy endpoints, the continuous variables will be summarized and analyzed as recorded on the case report forms (CRFs). If statistically significant imbalances are detected in the incidence of changes in DBS settings and outcome impacting medication use as well as the frequency of PRN drug or rescue medication between the initial study and the extension study, a Mixed-Effect Model Repeated Measure (MMRM) model will be used as the analysis method to compare the change in score from baseline between the initial study and the extension study for patients who received placebo in initial study (TIRCON2012V1) and the analysis will be based on observed cases. If no significant imbalance was detected, the paired t-test will be used as the analysis method and the last observed data will be used.

For the efficacy analysis on all patients who received DFP during the initial and the extension study, the last observation will be used to calculate the change from baseline for patients terminated early. As a sensitivity analysis, for early termination due to worsening of disease conditions or inadequate efficacy of the drug, as indicated in the CRF, the “worst score” method will be used for data imputation. That is, for continuous variables such as BAD total score at a particular time point, the worst score of all patients will be used to impute the missing data at that time point. For categorical variable such as responder, the worst category (treatment failure) will be assigned. For missing data due to missed visit, the last observation will be used to fill the void.

For BAD total score, if one or several component scores cannot be measured, then the same component score from the last visit will be carried forward and if it is also missing, the score from the next visit will be carried backward to fill the missing component score(s) before the total score is calculated.

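### In the all-patients responder analyses, a patient treated for worsening dystonia who stays to Visit 4 can still count as a responder, and no table scores this as failure

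*SAP*

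**What the plan says.** - **Response.** SAP section 4, all patients: for BAD, "responder analysis, responders defined as change in BAD total score to be" zero or less; for PGI-I, "responders are defined as patients whose conditions have not deteriorated". Neither has a condition on treatment added along the way. The results go to Tables 14.2.1.9 and 14.2.1.10 (by visit) and 14.2.1.16 (Visit 4, with a 95% CI).
- **Rescue.** Protocol 4.7 defines rescue medication as a new drug, or a dose change, that "has the potential to have an effect on dystonia symptoms and is provided because of a worsening of the" patient's condition. More than two rescue events lead to a discussion with the sponsor, not to automatic withdrawal. Protocol 5.1 also allows changes to DBS and pump settings when the investigator judges them necessary.
- **Populations (SAP 3.3).** ITT keeps these patients. PP is limited to completers who, among other conditions, "have no change in DBS and baclofen pump settings or medications that could have an impact on dystonia"; the next sentence adds a review of such medications for seriousness before database lock.
- **Failure rule (SAP 3.5).** A sensitivity analysis applies worst-score imputation "for early termination due to worsening of disease conditions or inadequate efficacy of the drug, as indicated in the CRF, the" trigger being the recorded reason for leaving. Responder status then becomes treatment failure.
- **Adjustment.** SAP section 4 accepts that DBS changes and dystonia-affecting medication "may confound the treatment effect assessment". The covariates for them enter only the comparison within former placebo patients, and only after a significant imbalance. The trend model for time on deferiprone has time as its sole term.

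**The concern.** Rescue is by definition a response to worsening, so it is recorded evidence that the patient deteriorated. If the added treatment brings the Visit 4 score back to baseline or below, the responder proportion credits that result to deferiprone.

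This matters because improved-or-unchanged is read as stabilisation in a progressive disease, and the all-patients analysis has no concurrent control in which the same effect could cancel. For the 44 former deferiprone patients the interval from baseline to Visit 4 is 36 months, which is long enough for treatment changes to accumulate.

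The SAP already holds that leaving because of worsening is failure. It has no matching rule for worsening that was treated and followed by staying.

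**Working it through.** **Step 1. Follow three kinds of patient through the rules.**

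| Patient | Main ITT (14.2.1.16) | PP (14.2.1.16a) | 14.2.1.16s as listed (PP) | 14.2.1.16s if run on ITT |
|---|---|---|---|---|
| A: worsens, leaves early for that reason | last observation decides | not in the set | not in the set | failure |
| B: worsens, treatment changed, stays, Visit 4 change 0 or less | responder | generally removed; responder if kept after review | as PP | responder |
| C: no treatment change, stays, Visit 4 change 0 or less | responder | responder | responder | responder |

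Patient B is not a failure in any column. Patient A is a failure only if the imputed table is run on ITT.

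**Step 2. The population of the imputed responder table.** SAP section 5 lists 14.2.1.16s as PP. SAP 4.3.2 bases the imputed analysis on ITT, but names only BAD change and PGI-I at Visit 4. The companion Table 14.2.1.15s is listed as ITT, and SAP section 7 reserves the suffix *a* for PP tables. The PP label may be a slip. As it stands, the failure rule has nobody to act on in the responder table, because PP contains only completers.

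**Step 3. Size per patient.** The plan states no figure to reproduce. SAP 3.2 gives 44 + 24 = 68 enrolled, which is the upper limit for ITT. One responder rescored as a failure moves the proportion by 100/68 = 1.47 points.

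**Step 4. Range under assumed rates.** The documents give neither a rescue rate nor a response rate. Let r be the fraction treated for worsening, p the response rate among the others, and m the fraction of treated patients who score 0 or less.

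- Rescue as failure: p(1 − r)
- ITT as written: p(1 − r) + rm, so the excess is rm
- Deleting treated patients: p, so the excess is pr

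Assume r = 0.10 to 0.30, p = 0.40 to 0.50 and m = 0.25 to 0.50.

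- Rescue as failure: 0.40 × 0.70 = 28% up to 0.50 × 0.90 = 45%
- ITT excess: 0.10 × 0.25 = 2.5 points up to 0.30 × 0.50 = 15 points, or about 2 to 10 of 68 patients
- Deletion excess: 0.40 × 0.10 = 4 points up to 0.50 × 0.30 = 15 points

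**Step 5. Can ITT and a deletion analysis agree while the failure-rule figure differs?** Assume 34 of 68 respond, which is 50.0% (exact 95% CI 37.6 to 62.4).

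| Treated for worsening (responders + non-responders) | ITT | Treated patients deleted | Rescue as failure (95% CI) |
|---|---|---|---|
| 3 + 4 | 50.0% | 31/61 = 50.8% | 31/68 = 45.6% (33.5 to 58.1) |
| 7 + 7 | 50.0% | 27/54 = 50.0% | 27/68 = 39.7% (28.0 to 52.3) |
| 10 + 10 | 50.0% | 24/48 = 50.0% | 24/68 = 35.3% (24.1 to 47.8) |

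They can. In the last two rows ITT and deletion coincide, while the failure-rule figure is 10.3 and 14.7 points lower.

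**The case against.** Analysing scores as recorded is a legitimate treatment-policy choice, and rescue-as-failure answers a different question. This stands, and it is why the main table should not change.

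The primary objective is safety. The all-patients responder result is a secondary proportion with a confidence interval and no success threshold. Rescue and as-needed use are tabulated, DBS and pump changes are listed, and worsening dystonia is summarised as an adverse event of special interest. This also stands and lowers the priority, but none of those outputs is linked to response across all patients.

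Protocol 5.1 asks that as-needed drugs be interrupted 30 to 90 days before visits. That limits the effect of occasional rescue on the Visit 4 score. It does not cover a drug continued as a regular regimen or a lasting change of settings.

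A reader might infer three stronger things that the documents do not support:

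- **That every such patient is deleted from PP.** The seriousness review in SAP 3.3 may keep some of them.
- **That ITT and PP are both pushed upward to a similar degree.** ITT can only equal or exceed rescue-as-failure on the same denominator. PP also drops non-completers, patients with major violations and patients whose treatment changed for reasons other than worsening, so its direction is not established.
- **That any as-needed use near Visit 4 signals failure.** Protocol 5.1 recognises patients on as-needed drugs since the start of the initial study.

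**Conclusion.** The gap is real. No listed all-patients efficacy table (14.2.1.1 to 14.2.1.17, with their variants) counts a patient who was treated for worsening and stayed as a non-responder. The one rule that assigns failure is tied to leaving, and its responder table is listed for a population with no early leavers. This conclusion rests on the text alone.

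The size is unknown. The figure of 1.47 points per patient assumes that all 68 enrolled patients are in ITT. The range of 2.5 to 15 points follows only from the assumed rates and is an illustration, not an estimate. Close agreement between ITT and PP would not rule out a material difference. Since efficacy is secondary, this is a modest-priority addition.

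**What to change.** 1. **Reconcile Table 14.2.1.16s to ITT**, in line with SAP 4.3.2, and say there that responders are included.
2. **Extend the SAP 3.5 failure rule in that table.** Also classify as a non-responder any patient with either of the following:
   - a documented worsening-driven start or increase of a dystonia-affecting medication, or a worsening-driven DBS or pump setting change, still in place at Visit 4;
   - rescue medication taken for worsening within the SAP's treatment impact period before the Visit 4 assessment, where a period is defined. The SAP defines periods for six drugs, while its own rescue table shell also shows diazepam.

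   Unchanged background as-needed use does not count.
3. **State the window.** For BAD it runs from the baseline used. For former deferiprone patients, apply the rule to the extension, and extend it to the initial study only if reasons for change were recorded there. Protocol 4.7 and 7.2.3.4 show that recording for the extension only. For PGI-I it runs from extension Visit 1, the reference point in Protocol 7.1.2.
4. **Report the number of such patients by former treatment group** beside Table 14.2.1.16, and leave that main ITT table unchanged.

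The cost is one relabelled sensitivity table with a derived flag, built for the extension from reasons the protocol already requires. The downside is a less favourable figure shown next to the main one.

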7 MEASUREMENTS AND EVALUATIONS

7.1 Efficacy Measurements

7.1.1 Barry-Albright Dystonia Scale

Dystonia is a neurological movement disorder in which sustained muscle contractions cause twisting and repetitive movements or abnormal postures. The Barry-Albright Dystonia (BAD) scale is a reliable and responsive measure for rating the degree to which dystonia interferes with function (27). A 5-point ordinal scale is used to rate the severity of dystonia in 8 body regions: eyes, mouth, neck, trunk, and each upper and each lower extremity. The individual scores are then summed to provide a total score that ranges from 0 to 32; the higher the score, the more severe the dystonia. See [Appendix 4](#).

For study TIRCON2012V1, a protocol was prepared by a group of experts to define a standardized way to administer and read the BAD scale, including a provocation test to better capture episodic or non-continuous symptoms. The administration of the BAD scale by the investigator or delegate is videotaped, and the videotape is sent to a central evaluator for objective assessment. The results will be sent back to the site, and will be entered by the study site staff into the eCRF.

In study TIRCON2012V1-EXT, the BAD scale will be administered at Visits 1, 2, 3, and 4 (or early termination visit).

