9.1.2 Secondary Endpoints

All patients:

- Change in the BAD total score from baseline (defined as prior to the start of deferiprone therapy) to Visit 4, as assessed by central evaluation of videotapes
- Proportion of patients with improved or unchanged BAD scale total score between baseline and Visit 4 (responder analysis)
- Change from baseline to Visit 4 in BAD scale score per body region (eyes, mouth, neck, trunk, and each upper and lower extremity), as assessed by central evaluation of videotapes
- Change in score on the PGI-I from baseline to Visit 4
- Proportion of patients showing an improvement on PGI-I at Visit 4 (responder analysis)

The time points for these efficacy endpoints are defined as follows:

- For patients who received deferiprone in the earlier study, the baseline visit of that study will be treated as the baseline visit of TIRCON2012V1-EXT as well. Thus, Visit 1 of the extension study (Week 0) will be Year 1.5, and Visit 4 (Week 78) will be Year 3.
- For patients who received placebo in the earlier study, Visit 1 of the extension study (Week 0) will be the baseline visit. Thus, Visit 4 (Week 78) will be Year 1.5.

Patients who received placebo in initial study:

For this group only, for each measure, the changes seen between the start and completion of study TIRCON2012V1 (i.e., following 18 months on placebo) will be compared against the changes seen between the start and completion of study TIRCON2012V1-EXT (i.e., following 18 months on deferiprone), as follows:

- Comparison of change in BAD total score from baseline to completion of the initial study vs. change in BAD total score from baseline to completion of the extension study
- Comparison of the proportion of patients with improved or unchanged BAD scale total score between baseline and completion of the initial study vs. the proportion with improved or unchanged BAD scale total score from baseline to completion of the extension study (responder analysis)
- Comparison of the change in BAD score per body region between baseline and completion of the initial study vs. change in BAD score per body region between baseline and completion of the extension study
- Comparison of change in PGI-I score from baseline to completion of the initial study vs. change in PGI-I score from baseline to completion of the extension study

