3.2 Determination of Sample Size and Study Power

There was no formal sample size and power calculation for this study. All patients who completed TIRCON2012V1 study were invited to enroll in the extension study. Among the 89 subjects randomized in TIRCON2012V1 study, 76 completed the study and 68 subjects were subsequently enrolled in this extension study (44 originally randomized to the deferiprone group and 24 in the placebo group).

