14.2.3 Analysis for Patients on DFP in Initial Study and the extension study	
Table 14.2.3.1	Comparison of change in BAD total score from baseline to month 18 for patients on DFP in initial study and patients on placebo in initial study but switched to DFP in the extension study – ITT population

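### In the 24 former placebo patients treatment is fully aliased with period, yet the SAP labels the period contrast as deferiprone versus placebo and plans no matching contrast in the 44 continuers

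*SAP*

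**What the plan says.** SAP section 4, under the former placebo patients, restricts the comparison: "For this group only, for each measure", the change over the placebo study ("i.e., following 18 months on placebo) will be compared against the changes seen") is compared with the change over the extension. Protocol 9.1.2 defines the same endpoint from "the changes seen between the start and completion of study TIRCON2012V1". SAP 3.2 gives the numbers enrolled as "44 originally randomized to the deferiprone group and 24 in the placebo group".

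- **Default tests** (SAP 3.5 and 4.3.1): a paired t-test for BAD and PGI-I and McNemar's test for responders, neither with covariates.
- **Conditional model** (SAP 3.5 and 4): if DBS changes or dystonia-related medication use differ significantly between the two studies, an MMRM is used for the BAD and PGI-I changes. It has terms for treatment, visit, their interaction, baseline score, DBS change, medication use and frequency of PRN or rescue use.
- **Labels**: the treatment term is defined as DFP versus placebo. Tables 14.2.2.2 and 14.2.2.5 carry p-values under a DFP-versus-placebo heading, and Table 14.2.2.9 reports a DFP-minus-placebo difference.
- **Error rate** (SAP 3.6): two-sided, "of 0.05 will be used as the significance level for the determination of statistical significance in all statistical tests".

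SAP section 5 has a block headed "14.2.3 Analysis for Patients on DFP in Initial Study and the extension study". Its one table, 14.2.3.1, compares BAD change to month 18 between the continuers in the initial study and the switchers in the extension, by a t-test.

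**The concern.** The order of treatments is the same in every switcher. The second-period change therefore differs from the first by drug and also by everything else that moved over those 18 months. PKAN is progressive, so patients enter the second period at a later stage. BAD is a "total score that ranges from 0 to 32", so patients who start high have less room to worsen. Scoring may drift. The extension is also open-label; this matters mainly for PGI-I, because BAD is rated centrally from video.

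Any of these can make the two changes differ without a drug effect. The SAP names only DBS and medication changes as possible confounders of this contrast. It is the only drug-versus-placebo contrast planned in this extension, and its output will carry p-values with a treatment label.

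The 44 continuers went through the same two periods on deferiprone in both, apart from a brief re-titration at the start of the extension (Protocol 3.3). Their own second-minus-first change is the natural companion figure, and it is not planned.

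**Working it through.** **No stated figure to reproduce.** SAP 3.2 says "There was no formal sample size and power calculation for this study". The group sizes agree: 24 + 44 = 68.

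**Can the planned model separate period from treatment?** No. VISIT indexes the visit within each study (months 6, 12 and 18), so each level occurs under both treatments. The treatment indicator is itself the period indicator. The baseline term partly adjusts for starting severity, but only when the MMRM is triggered.

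**Rejection rate with no drug effect.** Let D be a patient's second-period BAD change minus the first-period change, with mean s (a pure period difference) and standard deviation SD. The paired t-test rejects with probability P(|T| > 2.069), where T is noncentral t with 23 df and noncentrality s × √24 / SD. At s = 0 this is 5.0%. The values of s and SD are assumptions:

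| Period difference s | SD 3 | SD 4 | SD 5 |
|---|---|---|---|
| 0.5 point | 12.3% | 9.0% | 7.6% |
| 1 point | 34.7% | 21.7% | 15.6% |
| 2 points | 87.8% | 65.0% | 46.7% |

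Example: s = 1 and SD = 4 give noncentrality 1 × 4.899 / 4 = 1.22 and a rejection rate of 21.7%. The table takes all 24 switchers as contributing.

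**Ceiling alone.** In a simulation of 20,000 trials per scenario, scores were rounded and held within 0–32, with no drug effect. Assumptions: constant underlying worsening of 3 points per 18 months, patient-slope SD 1, measurement SD 1. The paired test rejected in 7.8% of trials at baseline mean 20 (SD 6), 17.6% at mean 24 (SD 5) and 28.1% at mean 26 (SD 5). Nearly all the excess favoured the drug.

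**What the continuers add.** In the same simulations, the difference in mean D between the 24 and the 44 rejected in 4.8–5.4% of no-drug-effect trials. With an assumed constant drug effect of 1.5 points and natural slowing from 3 to 2 points per period, the paired contrast averaged −2.5 and the between-group difference −1.5.

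**Cost in precision, equal SDs assumed.** The standard error is SD × √(1/24) = 0.204 SD for the paired test and SD × √(1/24 + 1/44) = 0.254 SD for the difference. The ratio is √(1 + 24/44) = 1.24. The 95% CI half-widths are 0.42 SD and 0.51 SD. The effect detectable with 80% power rises from 0.60 to 0.72 SD.

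**Is the continuers' contrast already in the outputs?** Only in part.
- Table 14.2.1.3 gives DFP-DFP mean change from the original baseline to month 36. Month 36 minus month 18 gives a second-period mean if the same patients are present at both visits, but no paired SD, CI or p-value.
- Table 14.2.1.9 counts responders against the original baseline, so a responder rate measured from month 18 cannot be recovered from it.
- The trend model fits one linear slope over time, which cannot show a difference between periods.

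**The case against.** The strongest reply is that the SAP already holds a check. Table 14.2.3.1 compares two groups that are both in their first 18 months on deferiprone, one in the first period and one in the second, and that come from a randomised split. It holds drug and time on drug constant, and so avoids the problem of a fading effect in continuers. This stands, and a reader who inferred that the continuers go unused would be wrong. The check is limited: it covers BAD total only, compares different patients, includes only completers who chose to continue (68 of 89 randomised), and never uses the continuers' second 18 months.

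A reader might also infer that the SAP credits every change to the drug. It does not. DBS and medication changes, with baseline score, are adjusted for when a significant imbalance is found, and no section sets a rule for claiming efficacy. What the SAP does is put a treatment label on the contrast.

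It is also fair to say that safety is the primary objective, efficacy is secondary, no power is claimed, and the randomised evidence belongs to the initial study. This limits the weight of the point. It does not change what the printed p-values can mean.

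**Conclusion.** The confounding is real and complete by design: no term in any planned analysis of the 24 switchers separates deferiprone from the second period. Its size is not known. The rejection rates rest on assumed SDs of 3 to 5 and assumed shifts of 0.5 to 2 points, with no anchor in the documents.

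Two stronger readings are tempting and unsupported. One is that the test is biased in favour of deferiprone: ceiling and slowing would act that way, but accelerating disease would act against it. The other is that a significant result could never be told apart from a period effect: Table 14.2.3.1 and the month-36 tables bear on that indirectly.

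Nor are the continuers a clean control. Their contrast isolates the period effect only if both groups share it and the deferiprone effect is constant over 36 months. A ceiling can also act unequally once the drug has shifted severity: in one simulated case the between-group difference was −1.44 against a true −1.5. It is therefore a supportive estimate. The change is worth making because the data are already collected and no planned output gives this contrast with its uncertainty.

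**What to change.** 1. In Tables 14.2.2.2, 14.2.2.5 and 14.2.2.9, relabel the result as a within-patient period comparison (deferiprone period versus placebo period).
2. Add to SAP section 14.2.3, beside the switchers' results, the continuers' paired period 1 versus period 2 change in BAD total and their responder rates, with period 2 measured from month 18.
3. Report the difference between the groups (24 versus 44) in mean paired BAD change with a 95% CI, as a supportive estimate. Two paired p-values side by side do not test whether the groups differ.
4. State its assumptions (a common period effect, and a deferiprone effect constant over 36 months) and cross-refer to Table 14.2.3.1 as the check that does not need the second one.

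The cost is a small amount of extra tabulation from data already collected. The supportive interval is wider than the paired one (SE about 1.24 times, with equal SDs), and the estimate is biased if the drug effect wanes or is delayed in continuers.
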